CLINICAL STUDY PROTOCOL

Protocol title: A Phase 2 Randomized, Double-Blind, Placebo-Controlled Study to Assess the Safety and Efficacy of Etrasimod in Adult Subjects with Eosinophilic Esophagitis

Protocol number: APD334-206 (C5041009)

Version: Amendment 3.0, dated 04 January 2023

Compound name or number: Etrasimod (APD334)

Study phase: 2

Indication: Eosinophilic esophagitis

EudraCT number: 2020-003226-23

Sponsor name: Arena Pharmaceuticals, Inc., a wholly owned subsidiary of Pfizer Inc.

Sponsor approval: This protocol was approved by the Sponsor's Responsible Medical Officer or delegate. The electronic signature manifest is appended.

Confidentiality Statement

This document contains confidential information of Arena Pharmaceuticals, Inc, a wholly owned subsidiary of Pfizer Inc. Unauthorized distribution, copying, or disclosure is strictly prohibited unless required by applicable law. Persons receiving this information must be notified that it is confidential and may not be further distributed, copied, or disclosed.

PROTOCOL HISTORY

Document	Amendment Type	Date
Amendment 3.0	Global	04 January 2023
Amendment 2.1	Regional	22 October 2021
Amendment 2.0	Global	20 October 2021
Amendment 1.1	Regional	24 March 2021
Amendment 1.0	Global	24 September 2020
Original 0.0	Not applicable	10 July 2020

PROTOCOL SYNOPSIS

Sponsor: Arena Pharmaceuticals, Inc.
Name of Investigational Study Drug: APD334 (etrasimod)
Protocol Title: A Phase 2 Randomized, Double-Blind, Placebo-Controlled Study to Assess the Safety and Efficacy of Etrasimod in Adult Subjects with Eosinophilic Esophagitis
Protocol Number: APD334-206
Phase: 2
Countries/Regions (planned): North America, European Union, Australia
Objectives: Primary: 
• To evaluate the effects of etrasimod on esophageal eosinophilia in adult subjects with active eosinophilic esophagitis (EoE)• To evaluate the dose-response relationship of 2 doses of etrasimod versus placebo in adult subjects with active EoE• To select an etrasimod dose based on efficacy and safety for continued development Secondary: 
• To evaluate the effect of etrasimod on dysphagia symptoms in adult subjects with active EoE
Study Design: 
This Phase 2, randomized, double-blind, multi-center study will evaluate the efficacy, safety, and pharmacokinetics (PK) of etrasimod compared with placebo in adults with active EoE. The study will consist of a Screening Period of up to 35 days, 24 weeks of double-blind treatment (Double-Blind Treatment Period), 28 weeks of active extended treatment (Extension Treatment Period), and 4 weeks of follow-up (Safety Follow-Up Period) for a total study duration of up to 61 weeks.
 
Eligible subjects will be randomized in a double-blind fashion (3:3:2 ratio) to etrasimod 1 mg, etrasimod 2 mg, or matching placebo once daily. Randomization will be stratified by baseline history of esophageal dilation (yes/no) and concurrent proton pump inhibitor (PPI) therapy (yes/no).
 
All subjects who complete the Double-Blind Treatment Period and meet eligibility criteria for the Extension Treatment Period may enter the Extension Treatment Period. Subjects who were in the etrasimod 1 mg or etrasimod 2 mg groups in the Double-Blind Treatment Period will continue the same etrasimod dose in the Extension Treatment Period. Subjects who were in the placebo group during the Double-Blind Treatment Period will be re-randomized (1:1 ratio) to etrasimod 1 mg or etrasimod 2 mg at entry into the Extension Treatment Period.
 
Subjects will have follow-up visits at 2 and 4 weeks after the last dose of study treatment after Week 52 or the Early Termination (ET) Visit.

Number of Subjects (planned):

Approximately 96 subjects are planned to be enrolled.

Eligibility Criteria for the Double-Blind Treatment Period:

Key Inclusion Criteria (Full Inclusion Criteria Are Provided in the Protocol)

- Men or women between 18 and 65 years of age at the time of informed consent (IC)
- Have an EoE diagnosis prior to screening and histologically active disease with an esophageal peak eosinophil count (PEC) of ≥ 15 eosinophils (eos)/high power field (hpf) (~ 60 eos/mm²) from any level (proximal, mid, or distal) of the esophagus at the Screening esophagogastroduodenoscopy (EGD)
- Have dysphagia, defined as solid food going down slowly or getting stuck in the throat with an average frequency of ≥ 2 episodes per week over 2 weeks (as documented using the Dysphagia Symptom Questionnaire (DSQ) during the Screening period)

Key Exclusion Criteria (Full Exclusion Criteria Are Provided in the Protocol)

- History of any of the following non-EoE conditions or procedures that may interfere with the evaluation of or affect the histologic, endoscopic, or symptom endpoints of the study:
 - a. Conditions that substantially contribute to esophageal eosinophilia (eg, eosinophilic gastritis or enteritis [ie, eosinophilic duodenitis or colitis] with esophageal involvement, achalasia, hypereosinophilic syndrome, Crohn's disease [CD] with esophageal involvement, esophageal infection [fungal, viral], eosinophilic granulomatosis with polyangiitis (formally known as Churg-Strauss Syndrome), pemphigus, with esophageal involvement, pill esophagitis, graft versus host disease, Mendelian disorders [eg, Marfan syndrome Type II, hyper-immunoglobulin E (IgE) syndrome, phosphatase and tensin homolog (PTEN) hamartoma tumor syndrome, Netherton syndrome, severe atopy metabolic wasting (SAM) syndrome])
 - b. Conditions that interfere with the evaluation of the esophagus (eg, esophageal varices with risk of spontaneous bleed, high-grade esophageal stenosis where an 8- to 10-mm endoscope could not pass through the stricture without dilation at the time of Screening EGD)
 - c. Conditions or procedures that substantially contribute to dysphagia (eg, histologically active Barrett's esophagitis, active erosive esophagitis Los Angeles Grade B or above, significant hiatal hernia [≥ 4 cm], esophageal resection)
- Undergone dilation of an esophageal stricture within 12 weeks prior to Screening EGD.
- Use of corticosteroids for the treatment of EoE within 8 weeks prior to Screening EGD.
- Discontinue, initiate, or change dosing (dosage/frequency) of the following therapies for EoE within 8 weeks prior to Screening EGD. Subjects on any of the following therapy need to stay on a stable regimen during study participation:

- d. Elemental diet
- e. EoE food trigger elimination diet
- f. PPI therapy

- Used any immunotherapy/desensitization including oral immunotherapy (OIT) or sublingual immunotherapy (SLIT) within 12 months prior to the Screening EGD.
Note: Stable (ie, ≥ 6 months prior to the Screening EGD) subcutaneous immunotherapy (SCIT) is permitted. Subjects on SCIT need to stay on a stable treatment during study participation.
- Used any of the following immunomodulatory therapies within the timeframes prior to Baseline as indicated below. The Medical Monitor should be consulted with any questions related to prior use of unlisted immunomodulatory therapies.

Time Frame	Therapies
Within 2 weeks	Antimetabolites (eg, AZA, 6-MP, MTX, 6-TG), calcineurin inhibitors (eg, cyclosporine, tacrolimus), MMF
Within 12 weeks (or 5 half-lives if shorter)	Anti-IL-5 antibodies (eg, mepolizumab, reslizumab, benralizumab), anti-IL-4/13 antibodies (eg, dupilumab), anti-IgE antibodies (eg, omalizumab), TNF α inhibitors (eg, infliximab), JAK inhibitors (eg, tofacitinib, oclacitinib)
Within 24 weeks	Anti-CD20 antibodies (eg, rituximab, ocrelizumab), anti-CD52 antibodies (eg, alemtuzumab), other cell-depleting therapies (eg, bone marrow transplantation, total body irradiation)
Any time prior to Baseline	Sphingosine 1-phosphate receptor modulators (eg, fingolimod, siponimod, ozanimod), natalizumab

AZA, azacytidine; IgE, immunoglobulin E; IL-4/13, interleukin-4/13; IL-5, interleukin-5; JAK, Janus kinase; 6-MP, 6-mercaptopurine; MMF, mycophenolate mofetil; MTX, methotrexate; 6-TG, 6-thioguanine; TNF α , tumor necrosis factor alpha

Eligibility Criteria for the Extension Treatment Period:

Inclusion Criteria

- Completion of the Week 24 study visit (including EGD) including subjects who discontinued study treatment due to lack of clinical efficacy and started rescue therapy between Weeks 16 and 24. Rescue therapy must be discontinued on the day etrasimod is initiated in the Extension Treatment Period.
- Compliance with study procedures during the Double-Blind Treatment Period as assessed by the Investigator
- No notable safety concerns during the Double-Blind Treatment Period, as determined by the Investigator
- Willing to comply with all study visits and procedures for the Extension Treatment Period

Test Product, Dose, and Mode of Administration:

Etrasimod 1 mg and 2 mg tablets taken once daily by mouth in the Double-Blind Treatment Period and the Extension Treatment Period.

Duration of Study:

The overall duration of the study will be up to 61 weeks, including:

- Up to 5-Week Screening Period
- 24-Week Double-Blind Treatment Period
- 28-Week Extension Treatment Period
- Safety Follow-Up Visits 2 and 4 weeks after the last dose of study treatment

Reference Therapy, Dose, and Mode of Administration

Matching placebo tablets taken once daily by mouth in the Double-Blind Treatment Period. There is no reference therapy (no placebo) during the Extension Treatment Period.

Efficacy Assessments:

Esophageal peak eosinophil count (PEC), EoE Histology Scoring System (HSS), DSQ, Food Avoidance Question (FAQ); Eosinophilic Esophagitis Endoscopic Reference Score (EREFS), Adult Eosinophilic Esophagitis Quality of Life (EoE-QOL-A), the Patient Global Impression of Change (PGIC), and Patient Global Impression of Severity (PGIS).

Primary efficacy endpoint:

- Percent change from Baseline in esophageal PEC at Week 16

Secondary efficacy endpoints:

- Absolute change from Baseline in DSQ score at Week 16
- Absolute change from Baseline in esophageal PEC at Week 16
- Proportion of subjects with esophageal PEC < 15 eos/hpf at Week 16
- Proportion of subjects with esophageal PEC \leq 6 eos/hpf at Week 16

A complete list of efficacy endpoints and definitions, as well as analysis methods will be provided in the Statistical Analysis Plan (SAP).

Pharmacokinetic Assessments:

Etrasimod plasma concentrations will be determined on Day 1 (predose and 4 hours \pm 15 minutes postdose) and before dosing at subsequent study visits and at the follow-up visits.

Collected blood for PK may also be used for profiling of drug binding proteins, bioanalytical method validation purposes, stability assessments, metabolite assessments, or to assess other actions of etrasimod with plasma constituents. Not all collected PK samples from placebo-treated subjects during the Double-Blind Treatment Period will be assayed.

Safety Assessments:

Safety will be assessed through the incidence of adverse events (AEs), clinical laboratory findings, 12-lead electrocardiograms (ECGs) (for first-dose monitoring, on treatment re-initiation after a defined period of treatment interruption, and at the start of the Extension Treatment Period, to be done predose and at 4 hours following the first dose), physical examinations, vital signs (measured hourly for at least 4 hours following the first dose), pulmonary function tests (PFTs), ophthalmoscopy and optical coherence tomography (OCT).

Statistical Methods:

CCI

Testing Strategy:

Unadjusted p-values for any hypothesis tests related to the comparisons of etrasimod dose group versus placebo will be reported. Estimated difference between etrasimod dose group and placebo as well as the associated 95% confidence intervals will be reported.

Statistical Analysis:

The primary and secondary endpoints will be analyzed using the Full Analysis Set (FAS) and demographic and safety analyses will be performed using the Safety Set. Other important statistical considerations, such as handling rescue medication/rescue procedure uses during study treatment, missing data imputation strategies, sensitivity analyses, and subgroup analyses will be described in the protocol and the SAP.

The endpoints of percentage change in esophageal PEC from Baseline to Week 16 and Week 24 will be analyzed using analysis of covariance (ANCOVA) model based on rank scores due to the skewed distribution of the data and possible outliers. The ANCOVA model will include treatment group and randomization stratification factors as factors and Baseline eosinophil PEC as a covariate. PEC after rescue medication/rescue procedure uses will be set to missing; all missing data will be imputed in the FAS using multiple imputation (MI) procedure as appropriate. Multiple results of ANCOVA (least square [LS] mean rank scores and LS mean rank score difference from placebo) for each MI dataset will be analyzed and reported along with final p-value using Rubin's method [1]. In addition, a descriptive summary of percentage change in esophageal PEC from baseline as well as the difference between treatment groups will be presented by treatment group. When applying the same ANCOVA model to key secondary continuous variables, no rank transformation will be used.

Proportion-based secondary endpoints (eg, histologic responders or symptomatic responders) at Week 16 will be analyzed in the FAS; subjects who use rescue medication or have a rescue procedure, or with missing data for any reason will be considered a "nonresponder" or "failure." The analyses will be performed using the Cochran-Mantel-Haenszel (CMH) method adjusted for randomization stratification factors. The number and percentage of subjects achieving the goal and the difference in proportion between treatment groups achieving the goal, along with p-value and the 95% CIs will be reported.

Longitudinal continuous endpoints will also be analyzed up to Week 24 using a linear mixed effects model. The model will include treatment group, visit, interaction of treatment-by-visit, and randomization stratification factors as factors and Baseline measure value as covariates. An unstructured covariance matrix will be specified for the within-subject measurements. LS means and LS mean differences between treatment group with unadjusted p-values and corresponding 95% CIs will be reported at each scheduled visit.

No hypothesis tests between treatment groups will be performed for endpoints measured during the Extension Treatment Period. Only descriptive statistics will be provided.

Continuous variables will be summarized using the number of observations, mean, SD, median, minimum, and maximum. Categorical variables will be summarized using frequency counts and percentages.

Subjects receiving any rescue therapy will have efficacy assessments after rescue therapy set to missing (continuous variable) or considered as treatment failures/non-responders at subsequent timepoints (dichotomous variables). Details and handling of rescue therapy for analysis will be contained in the protocol and SAP.

Safety Analysis:

All safety data will be listed and summarized by treatment group. All treatment-emergent AEs (TEAEs) will be coded using the Medical Dictionary for Regulatory Activities (MedDRA) and tabulated by System Organ Class and Preferred Term. Incidence of AEs, serious adverse events, adverse events of special interest, and AEs leading to study treatment discontinuation will be summarized and presented in descending order of frequency. In addition, details regarding risk-based safety analyses (eg, risk difference, hazard ratio) and exposure adjusted incidence rates will be described in the SAP. Laboratory parameters will be summarized by treatment group at each scheduled assessment timepoint using descriptive statistics.

Associated laboratory parameters such as hepatic enzymes, renal function, and hematology values will be grouped and presented together. Individual subject values will be listed and values outside of the standard reference range will be noted. Shift tables and analyses of changes from Baseline will be produced. The change from Baseline for each of the vital signs and ECG parameters will be summarized. Incidence of abnormal vital signs parameters and outlier ECG results will be tabulated.

Pharmacokinetic Analysis:

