Note: Stable (ie, ≥ 6 months prior to the Screening EGD) subcutaneous immunotherapy (SCIT) is permitted. Subjects on SCIT need to stay on a stable treatment during study participation.
6. Used any of the following immunomodulatory therapies within the timeframes prior to Baseline as indicated in [Table 1](#). The Medical Monitor should be consulted with any questions related to prior use of unlisted immunomodulatory therapies.

Table 1: Required Washout Period of Immunomodulatory Therapies

Time Frame	Therapies
Within 2 weeks	Antimetabolites (eg, AZA, 6-MP, MTX, 6-TG), calcineurin inhibitors (eg, cyclosporine, tacrolimus), MMF
Within 12 weeks (or 5 half-lives if shorter)	Anti-IL-5 antibodies (eg, mepolizumab, reslizumab, benralizumab), anti-IL-4/13 antibodies (eg, dupilumab), anti-IgE antibodies (eg, omalizumab), TNF α inhibitors (eg, infliximab), JAK inhibitors (eg, tofacitinib, oclacitinib)
Within 24 weeks	Anti-CD20 antibodies (eg, rituximab, ocrelizumab), anti-CD52 antibodies (eg, alemtuzumab), other cell-depleting therapies (eg, bone marrow transplantation, total body irradiation)
Any time prior to Baseline	Sphingosine 1-phosphate receptor modulators (eg, fingolimod, siponimod, ozanimod), natalizumab

AZA, azacytidine; IgE, immunoglobulin E; IL-4/13, interleukin-4/13; IL-5, interleukin-5; JAK, Janus kinase; 6-MP, 6-mercaptopurine; MMF, mycophenolate mofetil; MTX, methotrexate; 6-TG, 6-thioguanine; TNF α , tumor necrosis factor alpha

7. Use of moderate or strong inducers or inhibitors that inhibit or induce at least 2 of the following: cytochrome P450 (CYP) 2C8, CYP2C9, and CYP3A4 (eg, fluconazole, rifampin, enzalutamide) (Section 6.7.3) within 4 weeks prior to Baseline
8. Use of any investigational agent or device within 12 weeks prior Baseline
9. Have a known hypersensitivity to etrasimod or any of the excipients.

Exclusion criteria related to other medical history

10. Have any of the following conditions or risk factors:
 - a. Primary or secondary immunodeficiency syndromes (eg, hereditary immunodeficiency syndrome, acquired immunodeficiency syndrome)
 - b. History of organ transplant (except corneal transplant)
 - c. History of an opportunistic infection (eg, pneumocystis jirovecii pneumonia, cryptococcal meningitis, progressive multifocal leukoencephalopathy [PML])
 - d. History of disseminated herpes simplex or disseminated herpes zoster

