4.3. Eligibility Criteria for the Extension Treatment Period

Inclusion Criteria:

1. Completion of the Week 24 study visit (including EGD) including subjects who discontinued study treatment due to lack of clinical efficacy and started rescue therapy between Weeks 16 and 24. Rescue therapy must be discontinued on the day etrasimod is initiated in the Extension Treatment Period.
2. Compliance with study procedures during the Double-Blind Treatment Period as assessed by the Investigator
3. No notable safety concerns during the Double-Blind Treatment Period, as determined by the Investigator
4. Willing to comply with all study visits and procedures for the Extension Treatment Period

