6.7.2. Permitted Therapy

Stable treatment, dosage and/or dosing frequency of the following therapies:

- PPIs
- SCIT

- Diet therapy (eg, elimination diet, elemental diet)
- Inhaled/intranasal corticosteroids for the treatment of allergic comorbidities (eg, asthma, allergic rhinitis)
- Short course (eg, 7 days) or pulse corticosteroid therapy for exacerbation of a respiratory illness (eg, asthma)
- COVID-19 vaccines that are not categorized as live or live-attenuated viral vaccines and are approved or granted emergency use authorization

The Investigator must contact the medical monitor to discuss any changes to concomitant medications not listed here that could impact the outcome of the study.

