6.7.3. Prohibited Concomitant Therapy

The following therapies or procedures are prohibited during the study while on study treatment. However, in the event of an emergency, any needed medications may be prescribed without prior approval, but the Medical Monitor must be notified of the use of any prohibited medications immediately.

- Esophageal dilation
- Systemic corticosteroids (except pulse corticosteroid therapy, refer to Section 6.7.2)
- Oral or swallowed corticosteroids (for the treatment of EoE)
- SLIT or OIT
- Immunomodulatory agents
 - Examples: Antimetabolites (eg, azacytidine [AZA], 6-mercaptopurine [6-MP], methotrexate [MTX], 6-thioguanine [6-TG]), calcineurin inhibitors (eg, cyclosporine, tacrolimus), mycophenolate mofetil [MMF], S1P receptor modulators (eg, fingolimod, siponimod), anti-interleukin (IL)-5 antibodies (eg, mepolizumab, reslizumab, benralizumab), IL-4 and IL-13 antagonists (dupilumab), anti-IgE antibodies (omalizumab), anti-tumor necrosis factor alpha (TNF α) antagonists (eg, infliximab), anti-integrin antibodies (vedolizumab, natalizumab), Janus kinase (JAK) inhibitors (eg, tofacitinib, oclacitinib), anti-CD20 antibodies (rituximab, ocrelizumab), anti-CD52 antibodies (alemtuzumab)
- Any investigational drug other than the study treatment
- Class Ia (eg, quinidine, procainamide) and Class III (eg, sotalol, amiodarone) anti-arrhythmic drugs
- Live-attenuated virus vaccine (except for recommended and age-appropriate influenza, measles/mumps/rubella, or varicella vaccine) while on study treatment and within 4 weeks after the last dose of study treatment
- Moderate/strong inhibitors or inducers that inhibit or induce at least 2 of the following: CYP2C8, CYP2C9, and CYP3A4 (eg, fluconazole, rifampin, enzalutamide); for additional information refer to United States Food and Drug

Administration (FDA) *Drug development and drug interactions: Table of substrates, inhibitors and inducers* [48]

- Blood donations during the study and for 30 days after the last dose of study treatment
- Sperm or oocytes donation during the study and for 30 days after the last dose of study treatment

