6.7.4. Rescue Therapy

Any new medication or procedure used to treat new or worsened EoE symptoms is considered a rescue therapy. Rescue therapy should not be withheld if, in the opinion of the Investigator, failure to use/implement them would compromise the safety of the subject.

Subjects who discontinue between Week 16 and Week 24 due to lack of clinically meaningful efficacy will be provided the option to remain in the study. For these subjects, rescue therapy may be given until the end of the Double-Blind Treatment Period but must be discontinued upon entry in the Extension Treatment Period during which all subjects receive active treatment.

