9.4. Extension Treatment Period

9.4.1. Week 24 Visit

The Week 24 visit will be used to assess eligibility for the Extension Treatment Period and is considered the beginning of the Extension Treatment Period. During this visit, eligibility for

entry into the Extension Treatment Period will be confirmed (ie, meets eligibility criteria; Section 4.3).

At the Week 24 visit, vital signs should be measured first, followed by ECG, predose PK sample collection, study drug dosing at the study site, and first-dose cardiac monitoring (direct observation) for at least 4 hours in all subjects continuing in the Extension Treatment Period. Cardiac monitoring is required because there is a subset of subjects who will transition from placebo in the Double-Blind Treatment Period to an etrasimod dose in the Extension Treatment Period. Refer to Section 10.6.7.4 for detailed guidance on first-dose cardiac monitoring and subject discharge criteria postdose.

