APPENDIX 1: SCHEDULES OF ASSESSMENTS

Table 7: Schedule of Assessments – Screening, Double-Blind Treatment Period, and Safety Follow-Up Period

Evaluation	Screening Period	24-Week Double-Blind Treatment Period									Safety Follow-Up Period	
	D –35 to D –1	W0/D1	W2/ D15 (± 3) [Tele-health]	W4/ D29 (± 3)	W8/ D57 (± 5)	W12/ D85 (± 5) [Tele-health]	W16/ D113/ (± 5)	W20/ D141 (± 5) [Tele-health]	W24/ D169 ^a (± 5)	ET ^b	2-Week F-U Visit (± 3) [Tele-health]	4-Week F-U Visit (± 3)
Informed consent	X											
Inclusion/exclusion criteria	X	X							X			
Demographics, social and family history	X											
Medical history ^c	X	X										
Prior and concomitant therapies	X	X	X	X	X	X	X	X	X	X	X	X
Virology screen (HIV, HBV, HBsAg, HCV)	X											
Randomization/re-randomization		X							X			
eDiary training ^d	X											
eDiary monitoring ^e	X	X	X	X	X	X	X	X	X	X		
Adverse event assessment	X	X	X	X	X	X	X	X	X	X	X	X
Vital signs ^f	X ^f	X ^f		X	X		X		X	X		X
12-lead ECG ^g	X	X							X	X		
Physical examination ^h		X								X		
Pulmonary function test ⁱ	X								X	X		X

Evaluation	Screening Period	24-Week Double-Blind Treatment Period									Safety Follow-Up Period	
	D -35 to D -1	W0/D1	W2/D15 (± 3) [Tele-health]	W4/D29 (± 3)	W8/D57 (± 5)	W12/D85 (± 5) [Tele-health]	W16/D113/ (± 5)	W20/D141 (± 5) [Tele-health]	W24/D169 ^a (± 5)	ET ^b	2-Week F-U Visit (± 3) [Tele-health]	4-Week F-U Visit (± 3)
Ophthalmoscopy with OCT ^j	X								X	X		X
Pregnancy test ^k	X	X		X	X	X	X	X	X	X		X
CCI		■										
TBNK panel	X	X		X	X		X		X	X		X
Laboratory tests ^l	X	X		X	X		X		X	X		X
EGD and biopsies ^m	X						X		X	X		
PK assessments ⁿ		X		X	X		X		X	X		X
CCI		■					■		■			
Study drug dispensation ^p		X			X		X		X ^q			
Study drug accountability ^r			X	X	X	X	X	X	X	X		
In-person study drug dosing ^s		X		X	X		X		X			
Qualitative interview (optional) ^t									X			

^a For subjects who complete Week 24 and are eligible to enter the Extension Treatment Period, the Week 24 visit will be used to assess eligibility for the extension and may also serve as the Day 1 visit of the Extension Treatment Period. Subjects on placebo during the 24-Week Treatment Period will be re-randomized to study drug for the Extension Treatment Period (Section 6.4).

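### A subject rescued with a Table 1 immunomodulator in Weeks 16-24 may take etrasimod the day that agent stops, without the interval required at Day 1

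*Protocol*

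**What the plan says.** Extension inclusion 1, in the Protocol synopsis and in 4.3, covers "subjects who discontinued study treatment due to lack of clinical efficacy and started rescue therapy between Weeks 16 and 24". Its only condition on the rescue is "Rescue therapy must be discontinued on the day etrasimod is initiated in the Extension Treatment Period". Section 6.7.4 repeats the stop-on-entry rule and defines rescue broadly: "Any new medication or procedure used to treat new or worsened EoE symptoms is considered a rescue therapy".

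For the double-blind period, exclusion 6 and Table 1 (Protocol 4.2) set minimum intervals before Baseline:

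- 2 weeks: antimetabolites, calcineurin inhibitors and mycophenolate.
- "Within 12 weeks (or 5 half-lives if shorter"): anti-IL-5, anti-IL-4/13 and anti-IgE antibodies, TNF inhibitors and JAK inhibitors.
- 24 weeks: anti-CD20, anti-CD52 and other cell-depleting therapies.
- No prior use at all: S1P receptor modulators and natalizumab.

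Section 6.7.3 also bans immunomodulators, with this scope: "The following therapies or procedures are prohibited during the study while on study treatment".

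At Week 24, Table 7 marks a row named "Inclusion/exclusion criteria", and 9.4.1 says which criteria are meant: "entry into the Extension Treatment Period will be confirmed (ie, meets eligibility criteria; Section 4.3". Section 4.3 contains four inclusion criteria, no exclusion criteria and no washout.

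**The concern.** Read together, these rules set a required interval at Day 1 and none at Week 24 for the same agent. A subject who stopped study treatment for lack of efficacy is no longer on it, so the 6.7.3 ban does not reach rescue use in that gap. The ban applies again once etrasimod starts. That stops further doses of the other agent but does nothing about drug still acting.

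The stake is subject safety. Section 1.2 says that lymphocyte reduction may raise infection risk in some subjects. For a placebo subject the Week 24 visit brings the first dose of etrasimod, possibly on top of another immunomodulator, with less protection than the protocol itself sets for a first dose on Day 1.

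**Working it through.** The plan gives no figure of its own on this point. The check is a comparison of rules followed by calendar arithmetic.

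**Rules side by side**

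| | Day 1 | Week 24, after rescue |
|---|---|---|
| Governing text | Exclusion 6, Table 1 | 4.3 inclusion 1, 6.7.4 |
| Required interval | 14 days; 84 days (or 5 half-lives if shorter); 168 days; or never used | 0 days |

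**Inputs.** Week 16 is Day 113 ± 5 and Week 24 is Day 169 ± 5 (Protocol Table 7, SAP 6.4). The plan is for 96 subjects randomized 3:3:2, so placebo has 96 × 2/8 = 24.

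**Length of the rescue span**

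- Nominal: 169 − 113 = 56 days.
- Shortest: (169 − 5) − (113 + 5) = 46 days.
- Longest: (169 + 5) − (113 − 5) = 66 days.

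**Shortfall at the Week 24 visit**, if the last dose of the agent falls within that span

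- 2-week row: 0 to 14 days. It is met if the last dose was by Day 169 − 14 = Day 155.
- 12-week row: from 84 − 56 = 28 days (84 − 66 = 18 with windows) up to 84 − 0 = 84 days. It is met inside the span only if 5 half-lives is the shorter limit and has elapsed. The documents give no half-lives, so this cannot be computed.
- 24-week row: from 168 − 56 = 112 days (168 − 66 = 102 with windows) up to 168 days. It is never met.
- No-prior-use row: it cannot be met.

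**How many subjects.** The documents give no rate. Assume that 5-10% of subjects use the Weeks 16-24 rescue route and that 0-20% of those receive a Table 1 agent:

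- All arms: 96 × 0.05 × 0 = 0, up to 96 × 0.10 × 0.20 = 1.92.
- Placebo only: 0, up to 24 × 0.10 × 0.20 = 0.48.

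**The case against.** The strongest reply has four parts.

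**The case is hypothetical.** No text says that an immunomodulator was expected, supplied or recommended as rescue. This stands in part: the number may be zero, and the 24-week and no-prior-use rows are unlikely choices for EoE. The practical concern is the 2-week and 12-week rows. A reader might infer from SAP Appendix 4, which names anti-IL-5, dupilumab, omalizumab and other prohibited immunomodulators, that the plan authorises them as rescue. It does not. That appendix classifies intercurrent events and also takes in therapies that fall outside the rescue definition. It further says that therapy begun on or after the last study dose, in follow-up, is not counted as rescue.

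**Table 1 may protect baseline efficacy rather than safety.** The protocol does not state its purpose, and it sits beside the diet, PPI and corticosteroid rules. But exclusions 2 to 5 count back from the Screening EGD, while Table 1 counts back from Baseline and bars natalizumab and S1P agents at any time. That fits poorly with a purely histological purpose. A safety purpose remains an inference.

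**Safeguards exist.** Inclusion 3 asks the investigator for no notable safety concerns. Section 6.7.2 adds: "The Investigator must contact the medical monitor to discuss any changes to concomitant medications not listed here". Blood counts and the TBNK panel are drawn at Week 24 and later visits, and an independent monitor acts on low counts. It would be wrong to infer that these subjects go unmonitored. Yet none of this holds the first dose. Under Table 7 footnote l, Week 24 samples must be drawn before dosing but need not be read first. Treatment is interrupted at a confirmed lymphocyte count below 0.2 × 10⁹/L, whereas the entry bar at Screening is 0.8 × 10⁹/L.

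**Day 1 rules are not the natural standard for Week 24.** This is right as far as it goes. Carried over whole, the bar on any prior S1P modulator would exclude every subject already given etrasimod. The condition should therefore apply only to the rescue agent.

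**Conclusion.** The gap is real on the text, and closing it is a cheap safety improvement of low frequency, possibly affecting no subject. It rests on three things: the literal scope of 6.7.3 and 6.7.4, the reading of 9.4.1 that limits the Week 24 check to 4.3, and the inferred safety purpose of Table 1. The 0 to 2 of 96 range rests on assumed rates.

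Two stronger readings are not supported. One is that the same-day rule is wrong for all rescue. It looks deliberate for ordinary rescue: the 8-week corticosteroid exclusion is likewise not carried into the extension. The other is that efficacy results or the Week 24 dose selection are compromised. In the double-blind analyses, continuous data after rescue are set to missing and rescued subjects count as non-responders, while the extension is summarised without tests. At most, descriptive extension safety tables would contain such a subject.

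**What to change.** Add one sentence to 4.3 inclusion 1, to 6.7.4 and to the synopsis:

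> A subject whose rescue therapy was a Table 1 immunomodulator may enter the Extension Treatment Period only if that agent's Table 1 window (including the 5-half-lives alternative) has elapsed by the first extension dose, or with documented Medical Monitor approval before that dose; otherwise the subject does not enter the extension.

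Keep the same-day rule for PPI, swallowed corticosteroid, diet and dilation.

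A formal delayed-entry pathway is not worth building. Section 9.4.1 makes Week 24 the start of the extension, SAP 6.4 scores the DSQ on fixed study days, and the extension baseline histology would age during the wait.

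A SAP listing of days from last rescue dose to first extension dose is optional. SAP Section 14 tabulates class and drug name, not that interval, but the dates needed are already collected.

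The cost is one sentence in three places. The downside is that an assumed 0 to 2 of 96 subjects lose extension entry or need approval for it.
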